The purpose of this study is to evaluate the therapeutic efficacy of microdosing BurstDR[™] stimulation in spinal cord stimulation (SCS) patients with chronic intractable back and/or leg pain. Microdosing BurstDR[™] consists of periods during which stimulation is delivered with standard BurstDR[™] stimulation parameters alternated with periods during which no stimulation is being delivered. Previous results show that patients using standard BurstDR[™] can be programmed with microdosing with no changes to therapeutic efficacy (Vesper et. al, 2017). In this study we propose to evaluate therapeutic efficacy of BurstDR[™] microdosing, and determine optimal microdosing programming parameters in chronic pain patients, who are eligible for SCS therapy.

1.1 Objective(s)

- The primary objective is to evaluate the efficacy of BurstDR[™] microdosing stimulation in patients with chronic intractable back and/or leg pain with no prior history of SCS therapy.
- The secondary objectives are to evaluate the optimal microdosing program, evaluate the long term efficacy of BurstDR[™] stimulation on patient's pain intensity, and evaluate the improvements in quality of life, disability, anxiety, depression, catastrophizing and overall satisfaction.

1.2 Devices Used

The following devices will be used in this clinical investigation:

Device name	Model/Type	Manufacturer	Region/ Country	Investigational or Market Released
Abbott Invisible trial external pulse generator (EPG)	3599 (Base), 3032 (Header)	Abbott	US/OUS	Released
Abbott Invisible trial Clinician Programmer	3870, 3872	Abbott	US/OUS	Released
Abbott Invisible trial Patient Controller	3871, 3873	Abbott	US/OUS	Released
Abbot Percutaneous trial lead	31XX	Abbott	US/OUS	Released
Abbott Lead extension	33XX	Abbott	US/OUS	Released
Abbott Prodigy internal pulse generator (IPG)	3799	Abbott	US/OUS	Released
Abbott Prodigy MRI IPG	3772	Abbott	US/OUS	Released
Abbott Prodigy Charger	3730	Abbott	US/OUS	Released
Abbott Prodigy Patient Programmer	3856	Abbott	US/OUS	Released
Abbott Rapid Programmer programming device	3835	Abbott	US/OUS	Released
Abbott Proclaim IPG	3660, 3662	Abbott	US/OUS	Released
Abbott Clinician Programmer App	3874	Abbott	US/OUS	Released
Abbott Patient Controller App	3875	Abbott	US/OUS	Released
Abbott commercially available percutaneous leads	31X6, 318X, 314X, 315X, 316X	Abbott	US/OUS	Released
Abbott commercially available paddle leads	322X, 321X, 328X, 324X, 326X, 3240	Abbott	US/OUS	Released
Abbott Cinch™ Lead Anchor	1194	Abbott	US/OUS	Released
Abbott Swift-Lock™ Anchor	1192	Abbott	US/OUS	Released

Table 1: Identification of Devices under Investigation

1.3 Design

This is a prospective, open label, multicenter feasibility trial to evaluate the therapeutic efficacy of different BurstDR[™] microdosing patterns in patients with chronic intractable pain.

Subjects, eligible for SCS therapy, who are diagnosed with chronic intractable back and/or leg pain, will be considered for inclusion in this study. After baseline evaluation, subjects will undergo a SCS trial using the Abbott Invisible Trial system. During the trial implant phase, SCS leads will be implanted in the dorsal column based on physician discretion. According to standard clinical practices performed in the United States (US), the trial phase will last around 3-7 days. At the start of the trial phase, patients will be programmed with the first ON/OFF stimulation pattern (30 second STIM ON, 90 seconds STIM OFF). Patients who do not achieve adequate pain relief (at least 50% reduction in back and/or leg VAS from baseline) within the first 3-4 days will be reprogrammed to a new ON/OFF stimulation pattern (5 seconds ON/ 15 seconds OFF). Patients, who still do not achieve adequate pain relief within 2 to 3 days from reprogramming, will be reprogrammed to a continuous mode of BurstDR[™] stimulation and their trial evaluation will continue. These patients will be evaluated for an additional 2 days. At the end of the SCS trial, all subjects that experience at least 50% pain relief (according to average back and/or leg VAS) using one of the two microdosing burst stimulation paradigms will be considered further participation in the study. See Figure 1.

[figure not shown]

Fig 1: Representation of the decision making algorithm for the SCS trial phase of the study

Patients who have passed the trial phase and have received permanent implantation will be programmed based on the stimulation mode used for their trial success. Pain intensity, quality of life, disability, anxiety, depression, pain catastrophizing, satisfaction, and medication usage will be assessed at baseline, after SCS trial and at the 1, 3 and 6 month follow up. Adverse events will be collected throughout the study period.

During the month leading to the 1 month follow up visit, patients' pain relief will be evaluated on a weekly basis according to Figure 2. Briefly, patients who do not achieve adequate pain relief (greater or equal to pain relief achieved during the trial phase) will try lower stimulation ON/OFF ratios to determine the lowest possible stimulation ratio whilst maintaining adequate pain relief. This stimulation ON/OFF ratios will start from a ratio of 1:12 (Program 1) and increase to a potential ON/OFF ratio of 1:3 (Program 5) – Once the most optimal microdosing program is determined (as per algorithm in Figure 2), the patient will continue the rest of the study with that program. If inadequate pain relief is experienced anytime during the study, the BurstDR[™] microdosing parameters will be altered as per the algorithm in Figure 2.

[figure not shown]

Figure 2: Representation of the decision making algorithm for the SCS 1 month post permanent implant phase of the study

The total duration of the study is expected to be 2 years.

The clinical study will be conducted in up to 6 centers in the United States

Up to 60 subjects will be enrolled in this study.

1.4 Endpoints

There is 1 primary endpoint and 3 secondary endpoints in this clinical investigation.

1.4.1 **Primary Endpoints**

• Evaluate the change in pain intensity between baseline, trial and long-term follow up evaluations using the Visual Analog Scale (VAS) assessments.

1.4.2 Secondary Endpoints

- Evaluate the optimal microdosing program required to maintain optimal pain relief on a patient specific basis
- Evaluate the change in European Quality of life 5 Dimensions (EQ-5D) scores between baseline, SCS trial and follow up visits
- Evaluate the change in Oswestry Disability Index (ODI) scores between baseline, SCS trial and follow up visits
- Evaluate the change in Hospital Anxiety and Depression scale (HADS) scores between baseline, SCS trial and follow up visits
- Evaluate the change in Pain Catastrophizing Scale (PCS) scores between baseline, SCS trial and follow up visits
- Evaluate the change in Patient Global Impression of Change (PGIC) between SCS trial and follow up visits
- Evaluate the change in medication usage between baseline, SCS trial and follow up visits

1.4.3 **Descriptive Endpoint(s)**

Descriptive endpoints are reported using only summary statistics and no hypothesis tests will be performed.

- Optimal microdosing program
- Medication Usage

1.5 Study Population

The intended population of this clinical investigation consists of patients diagnosed with chronic intractable back and/or leg pain with no prior history of neuromodulation therapies.

1.6 Inclusion/Exclusion Criteria

1.6.1 Inclusion Criteria

- Subject is able to provide informed consent to participate in the study;
- Subject diagnosed with chronic intractable pain associated with back and/or limbs;
- Subject is 18 years of age or older;
- Subject has failed to respond to at least 6 months of conventional treatment which may include pharmacological treatment, physical therapy, epidural injections;
- Subject has a back and/or leg pain intensity of at least 6.0 cm out of 10.0 cm on the average back and/or leg pain VAS at baseline;
- Subject's medical record has been evaluated by the Investigator to ensure that the subject is a good candidate for a neurostimulation system;
- Subject is on stable pain medications with a total opioid for at least 28 days prior to enrolling in this study, and is willing to stay on those medications with no dose increase until the 3 month visit;
- Subject is willing to cooperate with the study requirements including compliance with the regimen and completion of all office visits;

• Female candidates of child-bearing potential agree to commit to the use of an effective method of contraception (including but not limited to sterilization, barrier devices, oral contraceptives, intrauterine devices (IUDs), condoms, rhythm method, or abstinence) for the duration of the study

1.6.2 Exclusion Criteria

- Subject has a current diagnosis of a coagulation disorder, bleeding diathesis, progressive peripheral vascular disease, post-herpetic neuralgia or uncontrolled diabetes mellitus;
- Subject is currently participating in a clinical investigation that includes an active treatment arm;
- Subject has been implanted with or participated in a trial period for a neurostimulation system;
- Subject has an infusion pump;
- Subject has evidence of an active disruptive psychological or psychiatric disorder as determined as per standard of care;
- Subject has a current diagnosis of a progressive neurological disease as determined by the Investigator;
- Subject is immunocompromised;
- Subject has an existing medical condition that is likely to require repetitive MRI evaluation in the future (i.e. epilepsy, stroke, multiple sclerosis, acoustic neuroma, tumor);
- Subject has history of cancer requiring active treatment in the last 12 months;
- Subject has an existing medical condition that is likely to require the use of diathermy in the future;
- Subject has documented history of allergic response to titanium or silicone;
- Subject has a documented history of substance abuse (narcotics, alcohol, etc.) or substance dependency in the 6 months prior to baseline data collection;
- Subject is a female candidates of child bearing potential that are pregnant (confirmed by positive urine/blood pregnancy test);
- Subject has life expectancy of less than 6 months;
- Subject is involved in an injury claim under current litigation

1.7 Enrollment

A patient becomes a subject once he/she has been fully informed about the study, has agreed to participate, signed & dated the consent.

1.8 Study Assessments

Subjects will undergo a baseline assessment to collect primary and secondary outcome measures prior to the SCS trial. Specifically, baseline assessments will include: pain rating as assessed by the VAS, quality of life as assessed by EQ-5D, disability as assessed by ODI, anxiety and depression as assessed by the HADS, and pain catastrophizing as assessed by the PCS. Medication usage will also be collected during the baseline visit.

Subjects will be implanted with trial SCS system according to clinical practice and practitioner's discretion. At the end of the SCS trial period, subjects who experienced a reduction of 50% or more in average pain back and/or leg VAS scores with one of the two microdosing stimulation paradigms will be offered permanent implant and further participation in the study. The same primary and secondary outcomes measures will be collected at the end of the SCS trial period as well as at the 1, 3 and 6 months follow up visit, with the inclusion of patient satisfaction as assessed by the PGIC. Programming parameters will also be assessed during these visits.

2 Introduction

This document is a clinical investigation plan (CIP) for the BOLD clinical investigation. This clinical investigation is intended to evaluate the therapeutic efficacy of microdosing BurstDR[™] stimulation in

spinal cord stimulation (SCS) patients with chronic intractable back and/or leg pain. This clinical investigation is sponsored by Abbott.

This clinical investigation will be conducted in accordance with this CIP. All parties involved in the conduct of the clinical investigation will be qualified by education, training, or experience to perform their tasks and this training will be documented appropriately.

3 Background and Justification for Clinical Investigation

Spinal cord stimulation (SCS) is increasingly being used as an alternative for the treatment of chronic, intractable pain. In a systematic meta-analysis of the literature, Taylor et al. (2006) reported that SCS reduces pain, improves quality of life, reduces analgesic use, allows some patients to return to work and may also result in significant cost savings over time, while having minimally significant adverse events in patients with neuropathic back and/or leg pain.

Patients receiving conventional tonic SCS (electrical pulses delivered in the 40-60Hz stimulation frequency range) experience paresthesia or a tingling sensation. Burst SCS is a newer paradigm that is currently approved worldwide. Burst stimulation eliminates or greatly reduces the incidence of paresthesia (Courtney et al. 2014), and it entails delivering groups of pulses called burst trains (A) repeated at a burst rate (B); within each burst train, several pulses are issued at an intra-burst rate (C) (See Figure 3). Individual pulses are characterized by a pulse amplitude (D) and pulse width.

[figure not shown]

Figure 3:

While the efficacy of standard burst stimulation parameters is known (Courtney et al. 2014, DeRidder et al., 2010, 2013), its comparison to more energy efficient settings is unknown.

Burst microdosing consists of delivery of intermittent doses of burst stimulation. Preliminary evidence supports that the therapeutic efficacy of burst microdosing results in a similar clinical outcome compared to standard burst stimulation (Vesper et al. 2017). Use of these new energy efficient stimulation parameters has the potential to prolong the battery life of a non-rechargeable, primary cell Implantable

Pulse Generator (IPG). It also has the potential to improve patient convenience by decreasing the frequency with which the patient has to recharge a non-primary cell IPG. In this study, we aim to evaluate the therapeutic efficacy of different BurstDR[™] microdosing patterns in patients with chronic intractable pain

4 Device(s) Under Investigation

4.1 Identification and Description of the Devices under investigation

4.1.1 Identification

Table 2: Identification	of Dovices under	Invoctigation
Table 2: Identification	of Devices under	Investigation

Device name	Model/Type	Manufacturer	Region/ Country	Investigational or Market Released
Abbott Invisible trial external pulse generator (EPG)	3599 (Base), 3032 (Header)	Abbott	US/OUS	Released
Abbott Invisible trial Clinician Programmer	3870, 3872	Abbott	US/OUS	Released
Abbott Invisible trial Patient Controller	3871, 3873	Abbott	US/OUS	Released
Abbot Percutaneous trial lead	31XX	Abbott	US/OUS	Released
Abbott Lead extension	33XX	Abbott	US/OUS	Released
Abbott Prodigy internal pulse generator (IPG)	3799	Abbott	US/OUS	Released
Abbott Prodigy MRI IPG	3772	Abbott	US/OUS	Released
Abbott Prodigy Charger	3730	Abbott	US/OUS	Released
Abbott Prodigy Patient Programmer	3856	Abbott	US/OUS	Released
Abbott Rapid Programmer programming device	3835	Abbott	US/OUS	Released
Abbott Proclaim IPG	3660, 3662	Abbott	US/OUS	Released
Abbott Clinician Programmer App	3874	Abbott	US/OUS	Released
Abbott Patient Controller App	3875	Abbott	US/OUS	Released
Abbott commercially available percutaneous leads	31X6, 318X, 314X, 315X, 316X	Abbott	US/OUS	Released
Abbott commercially available paddle leads	322X, 321X, 328X, 324X, 326X, 3240	Abbott	US/OUS	Released
Abbott Cinch™ Lead Anchor	1194	Abbott	US/OUS	Released
Abbott Swift-Lock™ Anchor	1192	Abbott	US/OUS	Released

4.1.2 Device Description and Intended Purpose

Abbott Invisible trial external pulse generator (EPG): a 16 channels, software controlled, battery powered, and external stimulator that generates the electrical pulses to be used during the trial phase of the study

Abbott Invisible trial Clinician Programmer: software compatible with iOS[™] App 8.1 or later to be used on iPad mini[™]; enables the clinician to program the Abbott Invisible trial EPG

Abbott Invisible trial Patient Controller: software compatible with iOS[™] App 8.1 or later to be used on iPad touch[™]; enables patient-controlled therapy adjustment of the Abbott Invisible trial EPG

Abbott Percutaneous trial lead: sterile stimulating electrode placed in the epidural space of the spinal cord and connected to the EPG

Abbott Lead extension: sterile extension that connects the pulse generator to the stimulating electrode **Abbott Prodigy:** a 16 channels, software controlled, rechargeable battery powered, internal stimulator to be used during the follow up phase of the study that generates the electrical pulses.

Abbott Prodigy MRI: a 16 channels, software controlled, rechargeable battery powered, internal stimulator to be used during the follow up phase of the study that generates the electrical pulses.

Abbott Prodigy Charger: The IPG Charging System provides the capability to recharge the IPG battery while stimulation is either on or off. The charging system has several main parts: AC line cord, AC power supply, power cable, and charger antenna. The charger transmits RF energy through the antenna to the IPG battery to recharge it.

Abbott Patient Programmer: the patient programmer allows subjects to adjust stimulation intensity and to select a different stimulation programs in the Prodigy MRI IPG.

Abbott Rapid Programmer: the rapid programmer enables the clinician to program the Prodigy IPG. **Abbott Proclaim internal pulse generator (IPG):** a 16 channels, software controlled, battery powered, internal stimulator to be used during the follow up phase of the study that generates the electrical pulses **Abbott Clinician Programmer App:** software compatible with iOS[™] App 8.3 or later to be used on iPad mini[™]; enables the clinician to program the Proclaim IPG

Abbott Patient Controller App: software compatible with iOS[™] App 8.1 or later to be used on iPad touch[™]; enables patient-controlled therapy adjustment of the Proclaim IPG

Abbott percutaneous leads lead: sterile stimulating electrode that are placed in the epidural space of the spinal cord and connected to the Proclaim or Protégé IPG

Abbott paddle leads: sterile stimulating electrodes that are placed in the epidural space of the spinal cord and connected to the Proclaim or Protégé IPG

Abbott Cinch[™] Lead Anchor: securing device designed to reduce lead migration and breakage Abbott Swift-Lock[™] Anchor: securing device designed to reduce lead migration and breakage

4.1.3 Device Handling and Storage

Sponsor requires all investigational products be stored, according to the labeling and Instructions for Use, in a secure area to prevent unauthorized access or use.

4.1.4 Identification

4.2 Devices Accountability

Device accountability not required in post market studies

5 Clinical Investigation Design

5.1 Clinical Investigation Design

This is a prospective, open label, multicenter feasibility trial to evaluate the therapeutic efficacy of different BurstDR[™] microdosing patterns in patients with chronic intractable pain.

[figure not shown]
Subjects diagnosed with chronic intractable back and/or leg pain, with no prior history of SCS therapy, will be considered for inclusion in this study. After baseline evaluation, subjects will undergo a SCS trial using the Abbott Invisible Trial system. During the trial implant phase, SCS leads will be implanted in the dorsal column based on physician discretion. According to standard clinical practices performed in the United States (US), the trial phase will last around 3-7 days. At the start of the trial phase, patients will be

programmed with the first ON/OFF stimulation pattern (30 second STIM ON, 90 seconds STIM OFF). Patients who do not achieve adequate pain relief (at least 50% reduction in back and/or leg VAS from baseline) within the first 3-4 days will be reprogrammed to a new ON/OFF stimulation pattern (5 seconds ON/ 15 seconds OFF). Patients, who still do not achieve adequate pain relief within 2 to 3 days from reprogramming, will be reprogrammed to a continuous mode of BurstDR[™] stimulation and their trial evaluation will continue. These patients will be evaluated for an additional 2 days. At the end of the SCS trial, all subjects that experience at least 50% pain relief (according to average back and/or leg VAS) using one of the two microdosing burst stimulation paradigms will be considered further participation in the study. See Figure 1.

Patients who have passed the trial phase and have received permanent implantation will be programmed based on the stimulation mode used for their trial success. Pain intensity, quality of life, disability, anxiety, depression, pain catastrophizing, satisfaction, and medication usage will be assessed at baseline, after SCS trial and at the 1, 3 and 6 month follow up. Adverse events will be collected throughout the study period.

During the month leading to the 1 month follow up visit, patients' pain relief will be evaluated on a weekly basis according to Figure 2. Briefly, patients who do not achieve adequate pain relief (greater or equal to pain relief achieved during the trial phase) will try lower stimulation ON/OFF ratios to determine the lowest possible stimulation ratio whilst maintaining adequate pain relief. This stimulation ON/OFF ratios will start from a ratio of 1:12 (Program 1) and increase to a potential ON/OFF ratio of 1:3 (Program 5) – Once the most optimal microdosing program is determined (as per algorithm in Figure 2), the patient will continue the rest of the study with that program. If inadequate pain relief is experienced anytime during the study, the BurstDRTM microdosing parameters will be altered as per the algorithm in Figure 2.

This confidential document is the property of Abbott and shall not be reproduced, distributed, disclosed or used without the express written consent of Abbott.

Figure 2: Representation of the decision making algorithm for the SCS 1 month post permanent implant phase of the study

The total duration of the study is expected to be 2 years.

The clinical study will be conducted in up to 6 centers in the United States.

Approximately 60 subjects will be enrolled in this study.

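### The post-implant titration text gives inconsistent directions: subjects without adequate relief go to lower ON/OFF ratios, yet the ladder starts at 1:12 and rises to 1:3

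*Combined protocol and SAP*

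**What the plan says.** Section 5.1 describes weekly evaluation of pain relief in the month before the 1-month visit, following Figure 2. It then summarises the rule in words. The trigger sentence reads "patients who do not achieve adequate pain relief (greater or equal to pain relief achieved during the trial phase) will try lower stimulation ON/OFF ratios", where adequate means at least the relief reached in the trial phase. Its stated purpose, worded the same way in section 1.3, is that such subjects "will try lower stimulation ON/OFF ratios to determine the lowest possible stimulation ratio whilst maintaining adequate pain relief".

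The sequence sentence follows directly: "This stimulation ON/OFF ratios will start from a ratio of 1:12 (Program 1) and increase to a potential ON/OFF ratio of 1:3 (Program 5". After an optimal program has been identified, "the patient will continue the rest of the study with that program". A closing sentence, beginning "If inadequate pain relief is experienced anytime during the study", refers any later change of parameters to Figure 2 and states no direction. Sections 1.3 and 6 repeat this paragraph.

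Three places bear on the starting program:

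- The sequence sentence names 1:12.
- Section 5.1 (also 1.3 and 6) says that implanted subjects "will be programmed based on the stimulation mode used for their trial success".
- Section 6.4.5 (Activation) refers only to standard programming techniques and gives no ratio.

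In the trial phase, subjects are first "programmed with the first ON/OFF stimulation pattern (30 second STIM ON, 90 seconds STIM OFF"). Those without adequate relief "will be reprogrammed to a new ON/OFF stimulation pattern (5 seconds ON/ 15 seconds OFF"). Only subjects who succeed on one of these two patterns are considered for the implant phase of the study.

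**The concern.** The two sentences that describe the titration point in different directions. One sends a subject with inadequate relief to a lower ratio; the other describes ratios that increase from the bottom of the ladder. The text fixes neither the starting program nor the step after adequate relief clearly enough to show which sentence governs.

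Two things depend on the rule. First, it produces the optimal microdosing program, which is the first-listed secondary endpoint (section 5.3.2) and is reported descriptively (section 5.3.3). Second, the chosen program carries forward unless it is altered, so it sets the stimulation in use when pain is scored at later visits for the primary endpoint (section 5.3.1). In a multicenter study, sites that act on different sentences could record different optimal programs for subjects with the same response. A table of optimal programs would then partly reflect how each site read the paragraph.

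**Working it through.** **Inputs.** Trial patterns of 30 s ON/90 s OFF and 5 s ON/15 s OFF, Program 1 at 1:12 and Program 5 at 1:3, all from section 5.1. The text gives no ratios for Programs 2 to 4.

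**Formulas.** ON/OFF ratio = ON ÷ OFF. Share of time ON = ON ÷ (ON + OFF).

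| Setting | ON/OFF ratio | Share of time ON |
|---|---|---|
| Trial pattern 1 | 30/90 = 0.333 (1:3) | 30/120 = 25.0% |
| Trial pattern 2 | 5/15 = 0.333 (1:3) | 5/20 = 25.0% |
| Program 1 | 1/12 = 0.083 | 1/13 = 7.7% |
| Program 5 | 1/3 = 0.333 | 1/4 = 25.0% |

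The plan's own description of the ladder is reproduced: 0.083 to 0.333 is an increase, 4-fold in ON/OFF ratio (0.333/0.083). In share of time ON it is 3.25-fold (0.25/0.0769), a difference of 25.0 − 7.7 = 17.3 percentage points. Both trial patterns already sit at the top of the ladder; they differ in cycle length (120 s against 20 s), not in ratio.

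**The sentences read under each possible start.**

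*Start at Program 1 (1:12).* A subject without adequate relief moves to the next program up. The first adequate program is the lowest listed ratio that keeps relief adequate. Trigger, sequence and purpose agree. The word *lower* does not: the step is upward, and the text lists nothing below Program 1 to try.

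*Start at the trial ratio (1:3).* A subject without adequate relief is sent, on the literal wording, to a lower ratio, which means less time ON. A subject with adequate relief is given no step in the text, although the stated purpose is to find the lowest adequate ratio. A sequence that starts at 1:12 and increases does not describe this path.

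**Which start applies.** The sequence sentence supports 1:12. The trial-success wording can be read as 1:3, because both qualifying patterns have that ratio; it can also be read as fixing the kind of pattern and leaving the ratio open. Section 6.4.5 does not decide the matter. Neither start makes every written sentence correct as it stands.

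**The case against.** The strongest defence is that this is an ascending search with one loose word. The only ratio that the text names as a start is 1:12, and the sequence is explicitly upward. In such a search, inadequate relief is exactly what should prompt the next step. *Lower* might mean only that the ladder lies at or below the trial ratio of 1:3. The paragraph also presents itself as a brief summary of Figure 2, which sites hold and which may set out the algorithm without ambiguity.

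Much of this stands. A reader might infer that a trigger of inadequate relief is incompatible with looking for the lowest adequate ratio. The documents do not support that, because the ascending reading makes the two compatible. A reader might also infer that a subject with adequate relief would never try a lower ratio. That requires activation at 1:3, which the text leaves open. Nor can anything be held against the plan because Figure 2 does not appear in the text available for this review.

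The defence does not remove the inconsistency. Reading *lower* as relative to the trial ratio may describe the ladder as a whole, but the sentence uses the word for what a subject does after inadequate relief. It also relies on a 1:12 start that the trial-success wording leaves in doubt. A clear Figure 2 would tell sites what to do, but it would not make the repeated sentences agree with each other.

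**Conclusion.** The concern holds as an inconsistency in the written direction of titration, together with an unclear starting program. It should be fixed. Confidence is moderate, because Figure 2 may already state the algorithm clearly.

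The range over which the written rule is unclear is the whole ladder, 7.7% to 25% of time ON. A reader might take the 17.3-point difference as the likely error in the optimal-program endpoint. It is not: the documents give no frequencies of program changes, and nothing shows that any site would follow the trigger sentence over the figure.

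The consequence is limited to how the recorded optimal program, and the stimulation in use at later visits, can be interpreted. The optimal program is summarised without a hypothesis test (section 5.3.3), and the study has no formal success criterion (section 7.6). It still deserves correction, since determining optimal programming parameters is a stated aim in the synopsis and section 7.1 says that the results may be used to generate a later study with formal testing.

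The conclusion assumes that the ratios are ON to OFF, as the text labels them, and that sites may act on the written paragraph as well as on the figure.

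**What to change.** Reconcile four items with one another: the trigger sentence and the sequence sentence (sections 1.3, 5.1 and 6), the trial-success programming wording (same sections), the activation wording (section 6.4.5), and Figure 2. The result should state once, and consistently:

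- the program in use at activation;
- the step after adequate relief;
- the step after inadequate relief, including later in the study.

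Which ratio, direction or threshold is right is for the sponsor and investigators to decide; none is proposed here.

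The cost is an amendment to three repeated paragraphs and one short section. It adds no visit or assessment. The Programming Form is already listed at activation and at the 1-, 3- and 6-month visits (sections 6.4.5 and 6.4.6). Those listings do not by themselves show that the weekly steps before the 1-month visit are recorded, so the sponsor should confirm this when revising the text.
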